8.7 Dosing Compliance and Test Article Exposure

Test article compliance will be determined by the total number of test article applications verified from the data in the subject diaries. Compliant subjects are defined as those who applied all three test article applications and had no other evidence of material dosing non-compliance.

Frequency tables of the total number of applications and the duration of treatment by treatment group will be presented for the mITT and PP populations.

8.8 Safety Analyses

8.8.1 Adverse Events

AE terms will be coded into SOC and PT using MedDRA Coding Dictionary version 19.0. Tabulations of the number and percent of unique subjects reporting each TEAE will be presented by SOC, PT, and treatment group for (a) AEs, (b) serious AEs, (c) AEs by maximum severity, (d) AEs by closest relationship to study drug and (e) AEs within treatment area. AEs will be counted only once for a subject within each PT and SOC. If a subject reports a PT multiple times with differing severities/relationships to study medication, the subject is counted once for the PT with the maximum severity and the closest relationship, respectively.

All adverse events will be listed.

8.8.2 Local Skin Reactions

The frequency of the individual LSRs will be tabulated by severity and treatment group at each visit. LSRs will also be summarized for each treatment group by the total score (sum of all LSRs) at Baseline, and Days 4, 8, 15, 29, and 57 and by the worst score of each individual LSR.

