1. BACKGROUND

Actinic keratoses (AKs) are common skin lesions which appear as scaly or crusty growths on the bald scalp, face, ears, lips, backs of the hands and forearms, shoulders, neck or any other areas of the body frequently exposed to the sun. The lesions appear as invisible or subclinical lesions as well as visible ones on the skin surface. Without treatment, AKs may spontaneously regress or progress to squamous cell carcinoma. It is unknown which AKs will develop into cancer so preventative treatment strategies are warranted. AK treatments include: topical medications (e.g., 5-fluorouracil, imiquimod, diclofenac, and ingenol mebutate), cryosurgery, combination therapies, chemical peels, laser surgery, and photodynamic therapy.

Ingenol mebutate is a pleiotropic effector which possesses a novel, dual mechanism of action as a topical therapy for skin cancer and pre-cancerous skin lesions. The anti-tumor activity of ingenol mebutate is associated with a direct cytotoxic effect on tumor cells and an enhanced innate and acquired immune response. Initially, ingenol mebutate rapidly induces necrosis, resulting in the debulking of locally-affected tumor cells. Secondly, it induces a tumor cell-specific innate immune response characterized by antibody dependent cellular cytotoxicity, which results in removal of residual disease. More recently, ingenol mebutate has been shown to also stimulate an acquired immune response through induction of tumor-specific cluster of differentiation CD8⁺ T-cell and CD4⁺ T-cell responses, resulting in further anti-tumor activity and possible long-term immunity.

Picato[®] (ingenol mebutate) gel is the first and only ingenol mebutate product approved by the FDA in 2012 for the topical treatment of AKs on the face and scalp (0.015% formulation) and on the trunk and extremities (0.05% formulation). The FDA approved regimen for ingenol mebutate gel, 0.015% for the treatment of AKs on the face and scalp is once-daily application of one unit dose tube for 3 consecutive days applied to one contiguous skin area of approximately 25 cm² (e.g., 5 cm x 5 cm).

A generic ingenol mebutate gel, 0.015% has been developed by the Sponsor for the topical treatment of clinically typical, visible, and discrete non-hyperkeratotic, non-hypertrophic AK lesions on the face and scalp.

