9.5 Unscheduled Visit(s)

A subject may have additional clinic visit(s), per discretion of the investigator, to manage any AEs or LSRs.

At this visit, the investigator or designee will:

- Query the subject about any changes in health status since the previous visit, including concomitant medications and therapies, and document the findings.
- Document LSRs, as applicable.
- Confirm the next visit.

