10.2 Local Skin Reactions

LSRs will be assessed in the Treatment Area and adjacent (2 cm border) surrounding skin at every clinic visit using a four-point ordinal scale where 0=absent, 1=mild (slight, barely perceptible), 2=moderate (distinct presence), and 3=severe (marked, intense). The following LSRs will be assessed:

- Erythema
- Flaking/scaling
- Crusting
- Swelling/edema
- Vesiculation/pustulation
- Erosion/ulceration
- Hyperpigmentation
- Hypopigmentation
- Scarring

These LSRs will be collected independently of AEs. Only LSRs that require medical intervention (e.g., prescription medication), require withholding of the application of the

test article), or extend beyond 2 cm outside of the Treatment Area will be documented as AEs. Any LSRs that are not listed above will be recorded as AEs.

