17.3.2 Safety Analyses

The analysis of safety will be conducted on the Safety population.

Dosing Compliance

Descriptive statistics will be used to summarize test article compliance for the mITT and PP populations. Measures of test article compliance will include the total number of applications as determined from the data recorded in the subject diaries. Compliant subjects will be defined as those who applied all three test article applications and had no other evidence of material dosing non-compliance.

Local Skin Reactions

Severity of LSRs (erythema, flaking/scaling, crusting, swelling/edema, vesiculation/pustulation, erosion/ulceration, hyperpigmentation, hypopigmentation, and scarring) will be recorded. LSRs will be summarized for each treatment group by frequency and severity of each individual LSR at Baseline, and Days 4, 8, 15, 29, and 57. LSRs will also be summarized for each treatment group by the most intense score of each individual LSR and by the total score (sum of all LSRs) at Baseline, and Days 4, 8, 15, 29, and 57.

Adverse Events

All AEs reported during the study will be listed, documenting course, severity, investigator assessment of the relationship to the test articles, and outcome. Verbatim terms on the eCRFs will be linked to preferred terms (PTs) and system organ class (SOC)

using the MedDRA mapping system. The PTs and SOC will then be tabulated. All reported AEs will be summarized by the number of subjects reporting AEs, SOC, PT, severity, and relationship to test article by treatment.

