8.12 Subgroup Analyses

No subgroup analyses are planned.

List of Tables:

Demographic and Baseline Characteristics

- 14.1.1 *Subject Disposition*
- 14.1.2 *Number of Subjects by Visit*
- 14.1.3.1 *Demographics (Safety Population)*
- 14.1.3.2 *Demographics (mITT Population)*
- 14.1.3.3 *Demographics (PP Population)*
- 14.1.4 *Baseline Vital Signs, Height, and Weight (mITT Population)*
- 14.1.5.1 *Baseline AK Count and Treatment Area (mITT Population)*
- 14.1.5.2 *Baseline AK Count and Treatment Area (PP Population)*
- 14.1.6 *Baseline Local Skin Reactions (Safety Population)*
- 14.1.7 *Medical History (mITT Population)*

Dosing Compliance and Exposure

- 14.2.1.1 *Dosing Compliance and Test Article Exposure (Safety Population)*
- 14.2.1.2 *Dosing Compliance and Test Article Exposure (mITT Population)*
- 14.2.2.3 *Dosing Compliance and Test Article Exposure (PP Population)*

Efficacy Data

- 14.3.1 *Complete Clearance Rates (PP and mITT Population)*
- 14.3.2.1 *AK Counts and Clearance Rates (mITT Population)*
- 14.3.2.2 *AK Counts and Clearance Rates (PP Population)*

Safety Data

- 14.4.1.1 *Local Skin Reaction – Erythema (Safety Population)*
- 14.4.1.2 *Local Skin Reaction – Flaking/Scaling (Safety Population)*
- 14.4.1.3 *Local Skin Reaction – Crusting (Safety Population)*
- 14.4.1.4 *Local Skin Reaction – Swelling/Edema (Safety Population)*
- 14.4.1.5 *Local Skin Reaction – Vesiculation/Pustulation (Safety Population)*
- 14.4.1.6 *Local Skin Reaction – Erosion/Ulceration (Safety Population)*
- 14.4.1.7 *Local Skin Reaction – Hyperpigmentation (Safety Population)*
- 14.4.1.8 *Local Skin Reaction – Hypopigmentation (Safety Population)*
- 14.4.1.9 *Local Skin Reaction – Scarring (Safety Population)*
- 14.4.2 *Summary of Adverse Events (Safety Population)*
- 14.4.3 *Treatment Emergent Adverse Events (Safety Population)*
- 14.4.4 *Treatment Emergent Adverse Events by Severity (Safety Population)*
- 14.4.5 *Treatment Emergent Adverse Events by Relationship to Test Article (Safety Population)*
- 14.4.6 *Treatment Emergent Adverse Events Occurring within the Treatment Area (Safety Population)*
- 14.4.7 *Concomitant Medications (Safety Population)*

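### No local skin reaction (LSR) summary compares a subject with their own Baseline, and the worst score is not limited to post-dose assessments, so pre-existing scale or crust can enter it

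*SAP*

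**What the plan says.** **Scoring.** Protocol 10.2 uses a 0-3 scale for nine items and states: "LSRs will be assessed in the Treatment Area and adjacent (2 cm border) surrounding skin at every clinic visit". The schedule of events includes Baseline. For unscheduled visits, Protocol 9.5 says: "Document LSRs, as applicable".

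**Disease in the scored area.** Inclusion criterion 4 requires 4 to 8 AKs, each at least 4 mm across, in the 25 cm² Treatment Area. Protocol Section 1 calls AKs "common skin lesions which appear as scaly or crusty growths". Flaking/scaling and crusting are two of the nine LSR items.

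**Analysis.** SAP 8.8.2 plans three descriptive summaries:
- By visit: "The frequency of the individual LSRs will be tabulated by severity and treatment group at each visit".
- Total score: "by the total score (sum of all LSRs) at Baseline, and Days 4, 8, 15, 29, and 57".
- Worst score: "by the worst score of each individual LSR", with no time window.

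Protocol 17.3.2 has matching text: "by the most intense score of each individual LSR and by the total score (sum of all LSRs) at Baseline", followed by the same post-dose days. The SAP's list of tables has a separate Baseline table (14.1.6, "Baseline Local Skin Reactions (Safety Population") and one table per item (14.4.1.1 to 14.4.1.9). None is titled as a shift or change table. The synopsis lists the LSR safety endpoint at Days 4, 8, 15, 29 and 57 only.

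**The concern.** A worst score is a maximum taken within each subject. If a sign was present before dosing, the maximum cannot fall below it when Baseline is included. The same holds when Baseline is excluded but the sign persists to any later visit. A vehicle subject scored 2 for scaling throughout and an active subject who went from 0 to 2 after dosing then look identical. The group-level Baseline table cannot separate them, because it does not show which subjects worsened.

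Safety is part of the study objective (Protocol Section 3, SAP Section 3). Listed LSRs become adverse events only if they need medical intervention, need dosing withheld or extend beyond 2 cm (Protocol 10.2, SAP 7.2.2). Local irritation short of those criteria is visible only in the LSR tables. In an equivalence study, dilution makes the two active products look more alike on tolerability.

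**Working it through.** **1. What the plan does with Baseline.** The documents give no LSR rate, threshold or test, so there is no figure to reproduce. The first check is a reading of the text.
- SAP Section 6 defines Baseline as pre-dose. SAP 7.2.1 defines treatment-emergent for adverse events by start on or after the first dose date. SAP 8.8.2 applies neither idea to LSRs within subject.
- The synopsis endpoint lists post-dose days only. Protocol 17.3.2 puts Baseline in the same sentence as the most intense score. SAP 8.8.2 detaches the worst score from any list of days. A programmer could therefore include or exclude Baseline and comply with the text either way.
- Nothing says whether scores from unscheduled visits, which Protocol 9.5 allows for managing LSRs, enter the worst score.

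**2. Size of the dilution.** Let b be the proportion with the sign at Baseline at a given severity cut-off, and t the proportion in whom treatment induces it. Assume that the two are independent, that b is the same in every arm, and that the Baseline sign counts towards the maximum (by inclusion or by persistence). Then

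P(worst at or above cut-off) = 1 - (1-b)(1-t)

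and the difference between arms 1 and 2 is (1-b)(t₁ - t₂). The relative loss is b, whatever the induced rates are.

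**3. Illustration.** All rates are assumed: t = 80% on active and 10% on vehicle (true difference 70 points), and 80% v 60% for Test v Reference (true difference 20 points).

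| b | Active (t = 80%) | Vehicle (t = 10%) | Difference (true 70) | Product with t = 60% | Difference (true 20) |
|---|---|---|---|---|---|
| 5% | 81.0% | 14.5% | 66.5 | 62.0% | 19 |
| 10% | 82.0% | 19.0% | 63 | 64.0% | 18 |
| 30% | 86.0% | 37.0% | 49 | 72.0% | 14 |
| 50% | 90.0% | 55.0% | 35 | 80.0% | 10 |
| 70% | 94.0% | 73.0% | 21 | 88.0% | 6 |

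For b = 50%: active 1 - 0.5 × 0.2 = 0.90; vehicle 1 - 0.5 × 0.9 = 0.55; difference 0.35 = 0.5 × 0.70.

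**4. What a shift table recovers.** Among subjects with no Baseline sign, b is 0 and the formula returns t, so the Baseline-score-0 row shows the undiluted contrast. Incidence above own Baseline takes unchanged disease out of the count. However, on a simple present/absent cut with all subjects in the denominator it equals (1-b)t, so its between-arm difference still carries the factor (1-b). The 0-3 scale softens this, because subjects at 1 or 2 can still worsen.

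**The case against.** The case on the other side is substantial, and most of it stands as a limit on the point.

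- **A reader might infer that Baseline is ignored.** It is not. It appears in the by-visit tables, the total score and Table 14.1.6. What is missing is any comparison within subject.
- **A reader might infer that disease is counted as drug reaction.** The documents do not support that. LSR scores carry no causality attribution, listed LSRs are collected separately from adverse events, and Protocol 10.2 does not tell the investigator to score an AK's own scale as an LSR. The text shows only that it can happen.
- **A reader might infer that at Day 57 uncleared subjects, mostly on vehicle, carry lesion scale scored as LSRs.** No section says so, and an uncleared lesion need not produce a scored sign.
- **b may be small.** Entry lesions must be non-hyperkeratotic and non-hypertrophic, and large mat-like AKs are excluded. At a moderate or severe cut-off, b could be well below its value at a score of 1 or more.
- **The overlap is documented for two of nine items.** The by-visit severity tables at Days 4, 8 and 15 remain for all of them.
- **Randomisation balances Baseline signs in expectation**, and mean change in total score can be read from the by-visit means, missing data aside.
- **No test, margin or decision rule uses LSRs.**

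Randomisation does not answer the dilution, however. A floor common to all arms still shrinks the difference between them, and group marginals cannot correct a per-subject maximum.

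**Conclusion.** The point holds in a limited form, at low severity. SAP 8.8.2 plans no within-subject comparison of LSRs with Baseline and leaves the worst-score window open. For flaking/scaling and crusting, pre-existing lesion scale or crust can therefore raise the worst-score incidence in every arm and attenuate the active-vehicle and Test-Reference contrasts.

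The relative attenuation equals b, which the documents do not give. It is slight if b is 5-10% and large if b is 30-70%. This rests on independence, a common b across arms, and Baseline signs counting towards the maximum. A reader might go further and conclude that a Test-Reference difference in irritancy is masked. The arithmetic does not support that: an assumed 20-point gap still shows as 6 points even at b = 70%, which is attenuation. Equivalence and superiority rest on complete clearance and are untouched.

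**What to change.** In SAP 8.8.2:

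1. Define the worst score of each LSR as the maximum over assessments after the first dose, and state that LSRs recorded at unscheduled visits are included. This removes Baseline from the maximum but not signs that persist after dosing, so step 2 is also needed.
2. Add Baseline-to-worst shift tables by arm, at least for flaking/scaling and crusting. Incidence of a post-dose score above the subject's own Baseline is an acceptable alternative. The shift table is preferable because its Baseline-score-0 row gives the undiluted contrast.
3. Keep the raw tables as planned. Change from Baseline in the total score is optional.

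The cost is SAP wording and programming. Baseline LSR scores are already collected, and no visit, assessment or sample size changes.

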8.8.3 Urine Pregnancy Tests

[figure not shown]
Results of UPT tests will be provided in a subject data listing.

8.8.4 Concomitant Medications and Concurrent Therapies/Procedures

Concomitant medications will be coded using the World Health Organization (WHO) Drug dictionary (version 01Sep2015). The medications will be tabulated by treatment group and Drug Class (pharmacological level, ATC3).

Prior and Concomitant medications and concurrent therapies/procedures will be provided in separate subject listings.

8.9 Sample Size

8.10 Protocol Deviations

Protocol deviations will be provided in a subject listing.

8.11 Interim Analysis

No interim analyses are planned.

8.12 Subgroup Analyses

No subgroup analyses are planned.

List of Tables:

Demographic and Baseline Characteristics

- 14.1.1 *Subject Disposition*
- 14.1.2 *Number of Subjects by Visit*
- 14.1.3.1 *Demographics (Safety Population)*
- 14.1.3.2 *Demographics (mITT Population)*
- 14.1.3.3 *Demographics (PP Population)*
- 14.1.4 *Baseline Vital Signs, Height, and Weight (mITT Population)*
- 14.1.5.1 *Baseline AK Count and Treatment Area (mITT Population)*
- 14.1.5.2 *Baseline AK Count and Treatment Area (PP Population)*
- 14.1.6 *Baseline Local Skin Reactions (Safety Population)*
- 14.1.7 *Medical History (mITT Population)*

Dosing Compliance and Exposure

- 14.2.1.1 *Dosing Compliance and Test Article Exposure (Safety Population)*
- 14.2.1.2 *Dosing Compliance and Test Article Exposure (mITT Population)*
- 14.2.2.3 *Dosing Compliance and Test Article Exposure (PP Population)*

Efficacy Data

- 14.3.1 *Complete Clearance Rates (PP and mITT Population)*
- 14.3.2.1 *AK Counts and Clearance Rates (mITT Population)*
- 14.3.2.2 *AK Counts and Clearance Rates (PP Population)*

Safety Data

- 14.4.1.1 *Local Skin Reaction – Erythema (Safety Population)*
- 14.4.1.2 *Local Skin Reaction – Flaking/Scaling (Safety Population)*
- 14.4.1.3 *Local Skin Reaction – Crusting (Safety Population)*
- 14.4.1.4 *Local Skin Reaction – Swelling/Edema (Safety Population)*
- 14.4.1.5 *Local Skin Reaction – Vesiculation/Pustulation (Safety Population)*
- 14.4.1.6 *Local Skin Reaction – Erosion/Ulceration (Safety Population)*
- 14.4.1.7 *Local Skin Reaction – Hyperpigmentation (Safety Population)*
- 14.4.1.8 *Local Skin Reaction – Hypopigmentation (Safety Population)*
- 14.4.1.9 *Local Skin Reaction – Scarring (Safety Population)*
- 14.4.2 *Summary of Adverse Events (Safety Population)*
- 14.4.3 *Treatment Emergent Adverse Events (Safety Population)*
- 14.4.4 *Treatment Emergent Adverse Events by Severity (Safety Population)*
- 14.4.5 *Treatment Emergent Adverse Events by Relationship to Test Article (Safety Population)*
- 14.4.6 *Treatment Emergent Adverse Events Occurring within the Treatment Area (Safety Population)*
- 14.4.7 *Concomitant Medications (Safety Population)*
